# Study Visits and Follow-up

Study visits that take place after the screening/randomization period should occur within +/- 7 days of the designated time interval for that study visit.

Screening evaluations will be completed within 14 days prior to randomization. Images and test results obtained for clinical patient management and before signing of informed consent do not need to be repeated and may be used for screening assessment provided images were taken within 28 days and tests conducted within 14 days of randomization. These evaluations will be the baseline values for patients randomized to the trial.

For patients randomized to Standard of care Sorafenib, study visits will take place at least once every 4 weeks until progression then every 8 weeks for as long as the patient remains on the trial. Additional patient clinical management visits may be scheduled between Q4 week visits as needed when initiating sorafenib treatment, to manage any adverse events and adjustments of sorafenib dosing or to adhere to local standard of care treatment requirements.

For Patients randomized to TheraSphere, the pre-treatment evaluations and TheraSphere treatment should take place within the first 4 weeks following randomization. After TheraSphere treatment, subsequent study visits will take place at least once every 4 weeks from randomization until progression then every 8 weeks thereafter.

Re-treatment of the same patient/tumor with further cycles of TheraSphere is allowed in case of detection during follow-up of a still treatable tumor progression. Patients can receive a subsequent TheraSphere administration in the absence of radiological progression criteria at investigator discretion Patients must meet initial eligibility criteria to receive subsequent treatments. A maximum of three (3) TheraSphere administrations are permitted in total

Follow-up visits for response assessment: In both arms, the first follow-up visit will take place at 2 weeks. Thereafter follow-up visits take place at least once every 4 weeks from randomization to week 24 or progression. After week 24, in the absence of progression, follow up visits will occur every 8 weeks from randomization to disease progression and include:

- ECOG Performance Status assessment
- Standard laboratory blood draw for CBC, differential, electrolytes, BUN, glucose, liver function test, coagulation panel, and α-fetoprotein biomarker
- QOL questionnaire (FACT-Hep)
- Adverse event reporting

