<sup>6 Pre-treatment evaluation is always done before the first TheraSphere treatment and prior to subsequent treatments as needed

<sup>7 TheraSphere must be administered within 4 weeks of randomization

<sup>8 Images taken up to 28 days in advance of randomization can be used for baseline images

 Imaging to be scheduled every 16 weeks from randomization at alternate Q8 week follow up visits

<sup>10 Document liver treatment medications only; medications used for supportive care do not require documentation

 A maximum of 2 re-treatments with TheraSphere are allowed following hepatic progression for lesions amenable to TheraSphere treatment

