# 9.1.1 Screening/Randomization (Days -14 to Day 0)

All screening and baseline evaluations must be completed within 14 days prior to randomization. CT/MRI scans obtained for clinical management prior to signing of the informed consent may be used for screening and baseline evaluations providing these scans were taken within 28 days before randomization and conform to the protocol image specifications in Section 9.2.17. External imaging will be accepted as long as performed with the necessary specifications, digitalized, and retrievable from internal radiological archive system. The quality of external imaging has to be adequate in order to capture liver volume measurement and mass calculations required at baseline. Test results obtained for clinical patient management and before signing of informed consent do not need to be repeated and may be used for screening assessment provided tests were conducted within 14 days of randomization. The date of screening is the date all screening procedures are completed.

The following activities will be completed during the screening period within 14 days prior to randomization.

- Informed Consent must be signed as described in Section 9.2.1.
- Patient demographic information will be collected as described in Section 9.2.2.
- Medical History information will be collected as described in Section 9.2.3.
- A physical examination as described in Section 9.2.4 will be done.
- Categorization of type of PVT as described in Section 9.2.5 will be done.
- 6. ECOG Performance Status will be assessed as described in Section 9.2.6.
- Child Pugh will be assessed as described in Section 9.2.7.
- Medication history & Prior treatment history will be obtained as described in Section 9.2.8.
- The liver tumor volume calculation will be completed as described in Section 9.2.9.
- 10. Baseline clinical laboratory tests, blood chemistry, hematology and coagulation, as described in Section 9.2.10 will be done.
- 11. A serum pregnancy test as described in Section 9.2.11 will be administered for all female patients of childbearing potential.
- 12. The patient's eligibility to participate will be assessed as described in Section 9.2.12.
- A baseline AFP level will be drawn as described in Section 9.2.13.
- 14. Baseline images for efficacy evaluation (Spiral CT of abdomen/pelvis and Spiral CT of chest) will be taken as described in Section 9.2.17. Images taken within 28 days prior to randomization may be used as baseline images.

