#### 9.1.3 Patients randomized to the Treatment Arm

#### 9.1.3.1 WEEKS 1-4 FOLLOWING RANDOMIZATION

The following study-related activities will be completed:

- 1. Complete appropriate clinical laboratory tests, including AFP, as described in Section 9.2.10 within 7 days prior to TheraSphere administration.
- 2. Conduct pre-TheraSphere evaluation within Week 2, as described in Section 9.2.16.1.2, and administer TheraSphere by the end of Week 4 to patients able to receive TheraSphere treatment as described in Section 9.2.16.1.7. For patients who are determined to be not treatable with

TheraSphere following the pretreatment evaluation, patients may begin sorafenib therapy as soon as possible.

- 3. Record details on the clinical assessments and administration of TheraSphere.
- Record any treatment and concurrent medications and any adverse events as described in Sections 9.2.18, 9.2.19 and 12.3.

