6.3 Baseline Assessments

Baseline for the following assessments is defined as the last assessment performed on or before the day of randomization.

- Informed Consent
- Inclusion/ Exclusion Criteria
- Demographics (age, gender, race, ethnicity)
- Medical history
- Physical examination
- Vital signs (heart rate [HR], respiration rate [RR], blood pressure [BP], aural temperature, height and weight)
- Disease and treatment history
- ECOG performance status
- Laboratory tests (hematology, coagulation, chemistry)
- Serum pregnancy test
- Child Pugh Score
- Categorization of PVT
- HCC tumor biomarkers- AFP
- Liver volume/mass and tumor burden
- FACT-HEP QOL

- CT/MRI of chest
- CT/MRI of pelvis/abdomen
- Stratification factors: AFP (400 ng/mL or >400 ng/mL) and participating trial site

Time from diagnosis of HCC will be calculated as follows:

Time from diagnosis of HCC (months) to randomization = (Date of Randomization – Date of Diagnosis)/30.4375.

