6.5.2 Adverse Events

Treatment Emergent Adverse Events (TEAEs) are AEs which were not present at the initiation of sorafenib or first angiogram or worsened in severity following treatment. If the imputed AE start date starts on or after the first dose of sorafenib or first angiogram and prior to 30 days after last dose of sorafenib or TheraSphere then it is considered a TEAE unless the AE was an ongoing event (end date of one AE matches start date of the next) that started prior to first dose of sorafenib or first angiogram and the grade did not worsen.

The investigator's verbatim term of the AEs will be mapped to system organ classes (SOC) and preferred terms using the MedDRA Version 14.0 dictionary (Medical Dictionary for Regulatory Activities). The investigator will use the NCI Common Toxicity Criteria for Adverse Events [CTCAE] (version 4.0) or the protocol specific criteria when no NCI CTC criteria are available for the adverse event to determine the severity of the AEs.

Adverse events related to sorafenib, device, and angiographic procedures are defined as those events recorded on the eCRF with relationship of possibly, probably, or definitely related.

The incidence of TEAEs will be the number of patients who had the AE (counted only once per patient) divided by the number of patients in the safety population and represented as a percentage. The incidence of AEs will be the number of times an event with the same preferred term occurs, counting worsening events only once. For worsening events, the AE end date of the earlier AE will be the same as the start date of the same AE with a higher severity.

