6.5.3 Clinical Laboratory Evaluations

Clinical laboratory results will be converted to SI units.

Laboratory data for safety analysis will be summarized as continuous summaries (ie, as absolute values, and change from baseline to each scheduled visit and end of study treatment in absolute values). Scheduled visits for hematology and coagulation

25

assessments will include Screening, Week 4, Week 8, Week 12, Week 16, Week 20, and Week 24, while scheduled visits for chemistry will include Screening, Week 2, Week 4, Week 8, Week 12, Week 16, Week 20, and Week 24. End of study treatment will be defined as from last dose of TheraSphere or sorafenib to 30 days after treatment.

Laboratory values will also be classified as normal (if value is within normal reference range) or lower/higher than normal (if value is either below or above the normal reference range).

Applicable laboratory values will also be classified using NCI CTCAE v4.0. Laboratory values within normal range will be categorized as either non-decreasing or non-increasing depending on the direction of the CTCAE grade (decreasing or increasing respectively).

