8.10.3 Clinical Laboratory Evaluations

Laboratory test values at each assessment and for change from baseline to each assessment will be displayed using summary statistics (n, mean, median, and standard deviation).

In addition, shift tables will be presented to display the shift in the normal range categories (L, normal [N], H) from baseline to the final evaluation. Baseline is defined as the latest non-missing value prior to randomization.

Shift table of laboratory assessments with CTCAE grade ≥3 that also worsened from baseline will be presented by visit for each laboratory parameter.

Shift table of baseline to each assessment by CTCAE grade will be summarized. Laboratory tests with CTCAE grades in two directions (increasing and decreasing) will be presented separately for each direction.

All clinical laboratory data will be presented in listings. Within each listing, laboratory values outside the normal ranges will be flagged as either high (H) or low (L).

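### Laboratory safety change is measured from a pre-randomisation baseline, while the SAP's own safety Day 1 and treatment-emergent AE rule start at first sorafenib dose or first angiogram

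*SAP*

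**What the plan says.** SAP 8.10.3 governs the laboratory change, normal-range shift and CTCAE shift tables, including the by-visit table of grade 3 or higher values that are worse than baseline. Its rule is: "Baseline is defined as the latest non-missing value prior to randomization". SAP 6.3 lists laboratory tests under a nearly identical rule: "Baseline for the following assessments is defined as the last assessment performed on or before the day of randomization". Both follow the protocol synopsis (Study Visits and Follow-up), which says of the screening assessments: "These evaluations will be the baseline values for patients randomized to the trial".

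The rest of the SAP's safety section uses a different origin. SAP 6.2.1 sets safety relative day 1 at first sorafenib dose (control) or first angiogram (treatment). SAP 6.5.2 defines treatment-emergent events as "AEs which were not present at the initiation of sorafenib or first angiogram or worsened in severity following treatment".

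SAP 6.5.3 lists the laboratory visits to be summarised: "scheduled visits for chemistry will include Screening, Week 2, Week 4, Week 8" and so on to Week 24. No rule in 6.5.3 or 8.10.3 sets aside values drawn before first treatment.

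The protocol also mentions a sample close to infusion. Section 9.1.3.1 lists it as an activity to be done: "Complete appropriate clinical laboratory tests, including AFP, as described in Section 9.2.10 within 7 days prior to TheraSphere administration". Section 9.2.16.1.8 instead leaves a new draw in that same week to the physician's discretion.

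**The concern.** A shift table in the Safety Population is read as a description of what happened after treatment. That population contains treated patients only, grouped by treatment received (SAP 8.3.2). If the baseline sample is taken weeks before treatment, any movement in liver tests over those weeks is counted in the shift.

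The same deterioration is then handled in two ways. An AE that begins after randomisation but before first dose or angiogram, and does not worsen, is not treatment-emergent. The laboratory value behind it does count as a change from baseline. The SAP neither explains nor reconciles this.

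Hepatic function is where this matters most. Protocol 5.3 cites a single-centre cohort with 19% grade 3/4 bilirubin toxicity after TheraSphere, and it lists hepatic decompensation among the serious events reported earlier. The laboratory tables are a natural place to look for that signal.

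**Working it through.** The plan states no figure on this point, so there is nothing to reproduce. The check is date arithmetic on the documents' own windows, followed by a reading of which values enter the tables.

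**Inputs**
- Baseline sample to randomisation: 0 to 14 days. Protocol 9.1.1: "All screening and baseline evaluations must be completed within 14 days prior to randomization".
- Randomisation to first sorafenib dose: up to 14 days (Protocol 9.2.16.2).
- Randomisation to first angiogram: up to 14 days (Protocol synopsis, Treatment Arm Study Treatment; also 9.1.3.1).
- Randomisation to TheraSphere infusion: up to 28 days. Protocol 3.2: "TheraSphere must be administered within 4 weeks of randomization".

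**Step 1: longest lag.** Maximum lag = maximum screening interval + maximum interval from randomisation to the event. The ±7-day visit allowance is left out.

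| Event | After randomisation | Lag from baseline sample |
|---|---|---|
| First sorafenib dose (control safety Day 1) | 14 | 14 + 14 = 28 days |
| First angiogram (treatment safety Day 1) | 14 | 14 + 14 = 28 days |
| TheraSphere infusion | 28 | 14 + 28 = 42 days |

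Measured to the SAP's safety Day 1, the arms differ by 28 − 28 = 0 days at the maximum. Measured to study treatment proper, they differ by 42 − 28 = 14 days.

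**Step 2: what enters the change score.** Let L be a laboratory value, B the baseline sample, D1 safety Day 1 and v a later visit. Then

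L(v) − L(B) = [L(D1) − L(B)] + [L(v) − L(D1)].

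The first bracket is change before treatment. Under 8.10.3 it is part of every later comparison. It can have either sign, so it can add to or mask change after treatment.

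**Step 3: values drawn before treatment.** Week 2 chemistry is nominally day 14, and SAP Table 3 accepts days 1 to 21. The control-arm schedule has sorafenib beginning at Week 2. For a patient who starts on day 14, a draw on any day from 7 to 14 is inside the visit allowance (14 − 7 = 7), is on or before first dose, and still becomes the Week 2 post-baseline value. In the TheraSphere arm the nominal Week 2 draw is 28 − 14 = 14 days before a Week 4 infusion. Angiography is also scheduled at Week 2, so that draw may come before or after safety Day 1.

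The SAP does not say which relative day the laboratory windows use, although Table 3 puts randomisation at day 0. If the windows ran from safety Day 1, early draws would no longer map to Week 2. The first bracket in Step 2 would remain.

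**Step 4: what re-anchoring would change.** Haematology and coagulation have no scheduled draw between screening and Week 4, and chemistry has only Week 2. Where no draw falls between screening and safety Day 1, baseline is still the screening value and the lag is still up to 28 days. Where a sample is taken in the 7 days before infusion, a pre-infusion baseline cuts the lag to infusion from up to 42 days to at most 7.

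**The case against.** The strongest case for the plan has four parts.

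1. A pre-randomisation baseline is what the protocol specifies. It is the same for both arms and is a defensible choice when randomised groups are compared. This stands for efficacy. It is weaker for laboratory tables built on treated patients by treatment received, in a SAP that starts its own safety clock at treatment.

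2. A reader might infer that TheraSphere is charged with a longer untreated period than sorafenib. The documents do not support that on the SAP's own safety start, where the limit is 14 days after randomisation in both arms. The extra 14 days appear only when the lag is measured to infusion. The interval from angiogram to infusion includes study procedures and possibly embolization, and the SAP tabulates events related to the angiographic procedure.

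3. A reader might picture a patient already at grade 3 bilirubin before infusion who is then counted as a toxicity at every later visit. That does not hold. Protocol 9.2.16.1.8 requires continued eligibility to be certified before administration, and eligibility includes Child-Pugh A (5–6 points). Bilirubin above 50 μmol/L scores 3, so with the minimum of 1 for each of the other four items the total is 3 + 4 = 7, which is grade B. The CTCAE cut-off is not in the documents, so this assumes that grade 3 lies above 50 μmol/L. In addition, the table is by visit, so a patient counts only at visits where the value is itself grade 3 or higher.

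4. Other outputs give a partial check. Clinically significant laboratory abnormalities can be AEs, and treatment-emergent AEs use the treatment-start anchor. All laboratory data are listed, and time to first treatment is summarised. This stands, and it limits the consequence. It does not correct the laboratory tables.

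**Conclusion.** The mismatch is real and of modest consequence. The laboratory baseline can be up to 28 days before the SAP's safety Day 1 in either arm and up to 42 days before TheraSphere infusion. Some values drawn at or before the start of treatment can be shown as post-baseline. These are the limits of the stated windows, not expected lags.

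Neither the size nor the direction of the effect on the tables can be computed, because the documents give no rate of laboratory deterioration before treatment. The documents do not support a claim of bias against TheraSphere. The treatment-emergent AE tables and the efficacy analyses are untouched. The affected tables are descriptive. The change is worth making because it is cheap and removes an unexplained inconsistency within the SAP, not because a conclusion of the trial depends on it.

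**What to change.** - In SAP 8.10.3, and for laboratory safety tests in 6.3, define baseline for Safety Population tables as the last non-missing value on or before safety Day 1 (first sorafenib dose or first angiogram). Count only later values as post-baseline.
- State in SAP 6.2.2 which relative day the laboratory windows use.
- Keep the pre-randomisation baseline for efficacy variables, including AFP, which SAP 6.4.3.4 places among them.
- As a descriptive supplement for TheraSphere patients only, show the CTCAE shift from the last available value before first infusion. Do not use it to compare arms: its baseline may be within 7 days of infusion, while a sorafenib patient's may be 28 days before first dose.
- Reconcile Protocol 9.1.3.1, which lists a draw in the week before infusion, with 9.2.16.1.8, which makes it discretionary. The supplement works with whatever value is available.

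The cost is SAP wording, one derived baseline flag and one extra table, with no new data collection. There are two downsides. Changes caused by the angiographic work-up fall into the baseline of the supplementary table, though they stay visible in the main table and the AE tables. For many patients, especially for haematology and coagulation, the new baseline will still be the screening value.

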8.11 Additional Safety Analyses

All the additional analyses described below will be performed on the Safety population.

A shift table comparing the baseline ECOG score to the ECOG score at each time-point will be summarized.

9 COMPUTER SOFTWARE

All analyses will be performed by Chiltern International using Version 9.2 or later of SAS® software. All summary tables and data listings will be prepared utilizing SAS® software.

The standard operating procedures (SOPs) of Chiltern International will be followed in the creation and quality control of all data displays and analyses.

11 APPENDICES

11.1 APPENDIX 1: VARIABLE DEFINITIONS

Age will be calculated as the randomization date minus the date of birth divided by 365.25 [Age=(ICF Date-DOB)/365.25].

Weight will be displayed in kilograms (kg), height will be displayed in centimeters (cm), and temperature will be displayed in Celsius (C). Weights, heights, or temperatures recorded in alternate units will be converted to the units being displayed using standard conversion formulas.

11.2 APPENDIX 2: STATISTICAL ANALYSIS and PROGRAMMING DETAILS

The SAS procedure LIFETEST will be used in the Kaplan-Meier analyses. Patients who did not have an event will be censored.

The following code will be used:

run;

class TRT VISIT SUBJID;
model CH=BASE TRT VISIT TRT*VISIT/s ddfm=kr;
repeated VISIT/type=UN subject=SUBJID;
lsmeans TRT*VISIT /slice=VISIT diff alpha=0.05 cl;

where TRT is the assigned treatment, VISIT is the visit based on the window mapping,

11.3 APPENDIX 3: Response Tables

CH is the change from baseline.

RECIST 1.1 Timepoint Response: Patients with target (+/- non-target) disease

| Target Lesions | Non-target Lesions | New Lesions | Overall Response |
|-------------------|-----------------------------|-------------|------------------|
| CR | CR | No | CR |
| CR | Non-CR/Non-PD | No | PR |
| CR | Not Evaluated | No | PR |
| PR | Non-PD or not all evaluated | No | PR |

| SD | Non-PD or not all evaluated | No | SD |
|-------------------------|-----------------------------|-----------|----|
| Not at all Evaluated | Non-PD | No | NE |
| PD | Any | Yes or No | PD |
| Any | PD | Yes or No | PD |
| Any | Any | Yes | PD |

Non-target Disease only

| Non-Target Lesions | New Lesions | Overall Response |
|-----------------------|-------------|------------------|
| CR | No | CR |
| Non-CR/Non-PD | No | Non-CR/non-PD |
| Not all evaluated | No | NE |
| Unequivical PD | Yes or No | PD |
| Any | Yes | PD |

11.4 APPENDIX 4: FACT-hep Questionnaire Scoring Rules

FACT-hep Scoring Guidelines (Version 4)

Instructions:* 1. Record answers in "item response" column. If missing, mark with an X

2. Perform reversals as indicated, and sum individual items to obtain a

score.

- 3. Multiply the sum of the item scores by the number of items in the subscale, then divide by the number of items answered. This produces the subscale score.
- 4. Add subscale scores to derive total scores (TOI & FACT-hep).

5. The higher the score, the better the QOL.

| Subscale Score | Item Code | Reverse item? | Item response | Item |
|---------------------|--------------------------|-------------------|--|-------------|
| PHYSICAL | GP1 | 4 - | | = |
| WELL-BEING | GP2 | 4 - | | = |
| (PWB) | GP3 | 4 - | | = |
| | GP4 | 4 - | | = |
| Scare range: 0-78 | GP5 | 4 - | | = |
| | GP6 | 4 - | | = |
| | GP7 | 4 - | | = |
| | | Divida b | - | ly by 7: |
| | | · | number of items = PWB subscale | answered: |
| SOCIAL/FAMILY | GS1 | 0 + | number of items | answered: |
| WELL-BEING | GS2 | 0 + 0 + | number of items | answered: |
| | GS2 GS3 | 0 + | number of items | answered: |
| WELL-BEING | GS2 GS3 GS4 | 0 + 0 + | number of items | answered: |
| WELL-BEING | GS2 GS3 GS4 GS5 | 0 + 0 + 0 + | number of items | answered: |
| WELL-BEING (SWB) | GS2 GS3 GS4 | 0 + 0 + 0 + 0 + | number of items | answered: |

| Multiply by 7: | |
|---------------------------------------|--|
| Divide by number of items answered: _ | |
| =SWB subscale score | |

| Protocol | TC_ | 104 |
|----------|-----|-----|

Statistical Analysis Plan

| GE1 | 4 | - | | = |
|-----|---|--|---|-----------------|
| GE2 | 0 | + | | = |
| GE3 | 4 | - | | = |
| GE4 | 4 | - | | = |
| GE5 | 4 | _ | | = |
| | | | | |
| GE6 | 4 | - | | = |
| | | | | |
| | | | Sum individud | al item scores: |
| | | | M | ultiply by 6: |
| | | Divi | de by number of it | tems answered: |
| | | | =EWB sub | scale score |
| | | | | |
| GF1 | | 0 | + | = |
| GF2 | | 0 | + | = |
| GF3 | | 0 | + | = |
| GF4 | | 0 | + | = |
| GF5 | | 0 | + | |
| GF6 | | 0 | + | |
| GF7 | | 0 | + | |
| | | - | | |
| | | | Sum individud | ıl item scores: |
| | | | | |
| | | | M | ultiply by 7: |
| | GE2 GE3 GE4 GE5 GE6 GF1 GF2 GF3 GF4 GF5 GF6 | GE2 0 GE3 4 GE4 4 GE5 4 GE6 4 GE6 4 GF1 GF2 GF3 GF4 GF5 GF6 | GE2 0 + GE3 4 - GE4 4 - GE5 4 - GE6 4 - Divi | GE2 |

[figure not shown]
=FWB subscale score

| Subscale Score | Item Code | Revei | rse item? | Item response | Item |
|----------------------|------------------|-------|-----------|----------------------|-------------|
| HEPATOBILIARY | Y C1 | 4 | - | | = |
| CANCER | C2 | 4 | - | | = |
| SUBSCALE | C3 | 0 | + | | = |
| (HCS) | C4 | 0 | + | | = |
| Score vange: 0-72 | C5 | 4 | - | | = |
| Xearo vango: II_ [] | C6 | 0 | + | | = |
| | Hep1 | 4 | - | | = |
| | Cns7 | 4 | - | | = |
| | Cx6 | 4 | - | | = |
| | HI7 | 4 | - | | = |
| | An7 | 0 | + | | = |
| | Hep2 | 4 | - | | = |
| | Hep3 | 4 | - | | = |
| | Hep4 | 4 | - | | = |
| | Hep5 | 4 | - | | = |
| | Hep6 | 4 | - | | = |
| | HN2 | 4 | - | | = |
| | Hep8 | 4 | - | | = |
| | | | | Sum individual item | scores: |
| | | | | | by 18: |

Document version 09Aug2017

Divide by number of items answered: _____

=HC Subscale score

